### 11.1 DETERMINATION OF SAMPLE SIZE

The sample size was determined by assuming a binomial distribution for the outcome of amputation to 3 years post treatment and then applying an adjustment for the maximum expected loss-to-follow-up. Based on preliminary data collected via retrospective studies that is on file with Stryker, the expected pooled amputation rate at 3 years for subjects meeting inclusion and exclusion criteria for this study is 10%.

An unadjusted chi-square test based on a 1-sided type 1 error rate of  $\alpha=0.025$  has 92% power to reject the null hypothesis that  $\pi_{amp} \geq 0.202$  in favor of the alternative hypothesis  $\pi_{amp} < 0.202$  (nQuery Advisor 7.0) with N=141 subjects. This sample size is increased by 29.5% to N=200 for account for loss-to-follow-up.

### 11.2 ANALYSIS PLAN BY CLINICAL INVESTIGATION ELEMENT AND EVALUATION

#### 11.2.1 Statistical Analysis

Evaluation elements are defined as the questions on the CRF/eCRF. The Statistical Analysis Plan (SAP) lists all evaluation elements and secondary elements which will be based on calculations between two or more evaluation elements.

All quantitative variables, including those based on calculations (secondary elements), will be analyzed with a case summary evaluation before the detailed characteristics and parameter can be evaluated. A case summary contains a listing of the number of valid cases/values, missing cases/values (if any) and total cases/values in the specific analysis. For quantitative variables the mean, median will be presented to summarize the average. The standard deviation, interquartile range (IQR) and range (based on maximum and minimum) will be calculated. A 95% confidence interval of the mean will also be constructed. A type 1 error  $\alpha=0.05$  will be used for all statistical tests of hypothesis. All assumptions in test of hypothesis will be investigated.

All qualitative variables, including those based on summaries (secondary elements), will be analyzed listing the proportions, frequencies, column and row totals and missing proportion (if any).

The SAP reflects this approach and specifies the variables characteristics (quantitative or qualitative) in detail together with the related analysis strategy. This also includes calculation and summaries based on primary elements and the required analysis.

#### 11.2.2 Primary Analysis / Endpoint

The primary effectiveness hypothesis will be tested on the basis of a confidence interval derived from a Kaplan-Meier analysis of cumulative amputation rates over time. The null and alternative hypotheses to be tested are as follows:

$H_0: \pi_{amp} \geq PG$  vs  $H_a: \pi_{amp} < PG$

$\pi_{amp}$  is the pooled 3-year cumulative rate of amputations, A Kaplan Meier survival estimate with confidence limits of the PG will be constructed for the time to amputation. These hypotheses will be tested by comparing the upper bound (UB) of a 1-sided 97.5% confidence interval (CI) at the 3-year to the target performance (PG). The null hypothesis ( $H_0$ ) will be rejected If  $UB < PG$ , and it will be concluded that the performance of the device(s) achieved the PG. This is approximately equivalent to specifying a 1-sided type 1 error rate of  $\alpha=0.025$ . A 1-sided type 1 error rate of  $\alpha=0.025$  rather than  $\alpha=0.05$  is specified to increase the robustness of the statistical evidence. A chart to depict the survival function with confidence limits will be presented.

#### 11.2.3 Secondary Analyses

Improvements in subject quality of life after surgery will be assessed by constructing 95% confidence interval for the mean change from baseline score in EQ-5D-5L and FAAM total and component scores to each annual visit with focus on the 3-year endpoint for consistency with the primary endpoint.

#### 11.2.4 Safety Analysis

All subjects enrolled in the study will be assessed for safety. AEs and other safety evaluations will be reported as frequencies and rates as appropriate, cumulative over the different follow-up schedules.

Safety endpoints will include all AEs, serious AE (SAE), device related adverse effect (DRAE), procedure related adverse effect (PRAE), serious device-related adverse effect (SDRAE), serious procedure-related adverse effect (SPRAE), unanticipated adverse device effects (UADEs) and type of surgical intervention as a consequence of the AE occurrence. For each type of AE and intervention type, total counts and per subject incident rates with 95% exact binomial confidence intervals will be reported. Counts of AE's will also be reported according to incidence time intervals.

#### 11.2.5 Additional Analysis

There are two types of fixation, external and internal. External fixation devices are always removed. Survival analysis of time to external fixation removal with Kaplan-Meier survival estimates and corresponding confidence limits will be presented. Internal fixation breakage will be reported as an AE.

Subgroup analysis of patient reported outcome improvement scores (EQ-5D-5L and FAAM) will be conducted for i.) patients with external fixation only, ii.) patients with internal fixation only, iii.) patients with external and/or internal fixation. In addition, subgroup analysis will be conducted by device type (HOFFMANN® LRF SYSTEM, SALVATION™ EXTERNAL FIXATION SYSTEM, SALVATION™ FUSION BOLTS AND BEAMS, SALVATION™ 2 MIDFOOT NAIL, THE SALVATION™ 3DI PLATING SYSTEM, T2® ICF SYSTEM, and VALOR™ ANKLE FUSION NAIL).

**MISSING DATA** For the primary endpoint analysis, subjects that have not experienced the event (i.e., amputation) at the last day of follow-up will be censored in the survival analysis. Patients that dropped out for any reason before their 3-year anniversary will also be censored at the last known date. A sensitivity analysis will be conducted that will exclude patients that dropped out from the study for reasons other than amputation prior to their three-year anniversary.

For the patient reported outcomes (EQ-5D and FAAM), statistical summaries will be computed only for available data. No imputation for missing data will be conducted.

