## 9.4 WITHDRAWAL CRITERIA

If, during the clinical investigation, a subject must be prematurely withdrawn, the procedures outlined in this section must be followed. These procedures should not interfere with the initiation of any new treatments that are necessary to treat a subject's condition. Information on all withdrawn subjects will be documented.

Subjects may be withdrawn from the clinical investigation for any of the following reasons:

- a. Subject Withdrawal: A subject may voluntarily withdraw from the clinical investigation at any time and for any reason. The subject should be asked when possible, and without any form of coercion, the reason for his/her decision. If the participant withdraws from the clinical investigation completely, then data collected up until the point of withdrawal will be included in the final analysis. Subjects who decline to continue to take part will be given the opportunity to discuss/inform the research team of the reasoning behind their decision not to take part.
- b. Lost to Follow-Up (LTFU): A subject will be considered LTFU after all reasonable efforts have been made to contact the subject and request his/her continued participation in the clinical investigation. All attempts to contact the subject must be documented and should include at least two attempts to contact the subject by phone and one attempt via a certified letter. Data collected up until the point where the subject is LTFU will be included in the final analysis.

- c. Amputation: The discontinuation of a subject's participation in the clinical investigation due to Amputation (below the knee or above the knee) All available information concerning the amputation AEs should be provided. Data collected up until the point of amputation will be included in the final analysis.
- d. Adverse Event: The discontinuation of a subject's participation due to an AEs that prohibits his/her continued participation must be fully explained. All available information concerning the AEs should be provided. Data collected up until the point of AE will be included in the final analysis.

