6.3 Withdrawal / Follow-up

The study allowed subjects to withdraw from the clinical investigation for any of the following reasons:

- a. Voluntary withdrawal by the subject;
- b. Subject was Lost to Follow-Up (LTFU);
- c. Amputation below the knee or above the knee;
- d. Adverse event that prohibited the subject from continued participation;
- e. Subject non-compliance to study protocol; and
- f. Other reason(s) that may have exposed the subject to unacceptable risk.

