7.5 Missing Data

No imputation of missing data will be conducted.

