15.1 All Table Shells

Table 1.1 Subject Disposition – ITT

Device	Pre-Op	Final F-up (Op- 1yr)	Post-Op (1 yr.)
SALVATION™ 3Di Plating			
Total			
Available Data			
Reason for Discontinuation			
Subject lost to follow-up			
Subject withdrew consent			
Adverse Event			
Other			
SALVATION™ External Fixation			
Total			
Available Data			
Reason for Discontinuation			
Subject lost to follow-up			
Subject withdrew consent			
Adverse Event			
Other			
SALVATION™ Fusion Bolts and Beams			
Total			
Available Data			
Reason for Discontinuation			
Subject lost to follow-up			
Subject withdrew consent			
Adverse Event			
Other			
SALVATION™ MIDFOOT NAIL			
Total			
Available Data			
Reason for Discontinuation			
Subject lost to follow-up			
Subject withdrew consent			
Adverse Event			
Other			

Device	Pre-Op	Final F-up (Op- 1yr)	Post-Op (1 yr.)
VALOR™ Nail			
Total			
Available Data			
Reason for Discontinuation			
Subject lost to follow-up			
Subject withdrew consent			
Adverse Event			
Other			
HOFFMANN® LRF SYSTEM			
Total			
Available Data			
Reason for Discontinuation			
Subject lost to follow-up			
Subject withdrew consent			
Adverse Event			
Other			
T2® ICF SYSTEM			
Total			
Available Data			
Reason for Discontinuation			
Subject lost to follow-up			
Subject withdrew consent			
Adverse Event			
Other			

Table 1.2 Subject Eligibility

Table 1.3 Subject Accounting and Follow-up Compliance – ITT

Device	Pre-op	1 Year	Final Visit
	N	N	N
SALVATION™ 3Di Plating System			
Theoretical			
Deaths (cumulative)			
Failures (cumulative)			
Withdrawn (cumulative)			
Expected			
Actual ¹			
% Follow-up ¹			
EQ-5D Score			
FAAM Score			
SALVATION™ External Fixation			
Theoretical			
Deaths (cumulative)			
Failures (cumulative)			
Withdrawn (cumulative)			
Expected			
Actual ¹			
% Follow-up ¹			
EQ-5D Score			
FAAM Score			
SALVATION™ Fusion Bolts and Beams			
Theoretical			
Deaths (cumulative)			
Failures (cumulative)			
Withdrawn (cumulative)			
Expected			
Actual ¹			
% Follow-up ¹			
EQ-5D Score			
FAAM Score			
SALVATION™ MIDFOOT NAIL			
Theoretical			
Deaths (cumulative)			
Failures (cumulative)			
Withdrawn (cumulative)			
Expected			
Actual ¹			
% Follow-up ¹			
EQ-5D Score			
FAAM Score			
VALOR™ Nail			
Theoretical			
Deaths (cumulative)			
Failures (cumulative)			

Withdrawn (cumulative)			
Expected			
Actual ¹			
% Follow-up ¹			
EQ-5D Score			
FAAM Score			
¹Any data point available at follow-up			

Table 1.4 CIP Deviations

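### EQ-5D-5L and FAAM change summaries are likely to leave out amputees at visits after the amputation, and the SAP tables do not show this

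*Protocol*

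**What the plan says.** **Withdrawal.** CIP 9.4 opens its list with "Subjects may be withdrawn from the clinical investigation for any of the following reasons". Item c is discontinuation of "participation in the clinical investigation due to Amputation (below the knee or above the knee"), followed by "Data collected up until the point of amputation will be included in the final analysis". SAP 6.3 also lists "Amputation below the knee or above the knee" and gives adverse event as a separate reason.

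**Summaries.** CIP 11.2.3 plans 95% confidence intervals for mean change in EQ-5D-5L and FAAM at each annual visit, with emphasis on 3 years. SAP 9 and 9.2 keep the change summaries and the confidence intervals, and the shells for Tables 3.1 and 3.2 report them by device at baseline, final visit and 1 year. Neither document restricts the mean to subjects with a retained limb.

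**Missing data.** For these scores, CIP 11.2.5 says that "statistical summaries will be computed only for available data" and adds "No imputation for missing data will be conducted". SAP 7.5 states "No imputation of missing data will be conducted". The CIP's only dropout sensitivity analysis concerns the primary endpoint.

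**Accounting.** Under "Reason for Discontinuation", the Table 1.1 shell offers lost to follow-up, withdrawn consent, adverse event and other. It has no row for amputation, death or sponsor termination.

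**The concern.** A subject withdrawn at amputation has no EQ-5D-5L or FAAM score at later visits. That gap is caused by the event that defines failure on the primary endpoint, so the subjects left in the mean are a selected group. If amputees fare worse on these scores, the mean improvement looks better than it would for everyone treated. A device with more amputations could even show a better mean change than one with fewer.

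The reader of Tables 3.1 and 3.2 would not see this. The tables carry no note on who is missing or why, and in Table 1.1 an amputation can be filed only under adverse event or other, together with unrelated losses. The scores are the first-listed secondary performance endpoint, and under the SAP they are reported device by device in a cohort of about 42.

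**Working it through.** The documents give no expected EQ-5D or FAAM change, no standard deviation and no post-amputation score, so there is no plan figure to reproduce.

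**Inputs from the documents**
- Expected 3-year amputation rate: 10% (CIP 11.1).
- Literature rate: 49/285 = 17.2%, at mean follow-up of 29.5 months (CIP 8).
- About 42 subjects implanted (SAP 4.1), and none reached 3 years (SAP 9.1).

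**Assumptions**
- Mean gain of 15 points on a 0–100 scale in retained limbs, and a mean change of 0 to −10 in amputees. The gap is then 15 to 25 points.
- No amputee contributes a score at the visit.
- For the 1-year figures, both rates are treated as 3-year rates with constant hazard.

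**Formula.** With amputation proportion a, the all-subject mean is (1 − a) × 15 + a × m, where m is the amputee mean. The overstatement is 15 minus this, which equals a × gap.

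**At the CIP's 3-year focus**

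| a | all-subject mean, m = 0 | all-subject mean, m = −10 | overstatement |
|---|---|---|---|
| 10% | 13.5 | 12.5 | 1.5 to 2.5 |
| 17.2% | 12.4 | 10.7 | 2.6 to 4.3 |

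**At 1 year, where the SAP's dated score shells stop**
- 1 − (1 − 0.10)^(1/3) = 3.5%, and 1 − (1 − 0.172)^(1/3) = 6.1%.
- Expected amputees among 42: 42 × 0.0345 = 1.4, and 42 × 0.0610 = 2.6.
- Overstatement at 3.5%: 0.0345 × 15 = 0.5 to 0.0345 × 25 = 0.9 points.
- Overstatement at 6.1%: 0.0610 × 15 = 0.9 to 0.0610 × 25 = 1.5 points.
- Amputations clustered early after surgery would raise these figures.

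**Per device.** Spread evenly over the seven named systems, 42 subjects give about 6 each. This is an assumption, since a subject may receive more than one system. If one of six is an amputee without a score, the six-subject mean is (5 × 15 + 0)/6 = 12.5 or (5 × 15 − 10)/6 = 10.8, against a reported 15. The overstatement is 2.5 to 4.2 points.

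**Share improved.** If 60% of retained-limb subjects improve (assumed), counting amputees as not improved gives 0.60 × 0.90 = 54% and 0.60 × 0.828 = 50% at the 3-year rates. At the 1-year rates it gives 0.60 × 0.965 = 58% and 0.60 × 0.939 = 56%.

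**Direction.** The sign depends on the gap. With no gap there is no overstatement, and if amputees gained more than the others, the mean would understate improvement.

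**The case against.** The best defence is that a retained-limb summary, with amputation reported separately, is a legitimate choice. FAAM measures foot and ankle function, and its meaning after loss of the operated limb is unclear. The SAP does report the failures: amputation counts by visit (9.1), an amputation status row in Table 3.3, cumulative deaths, failures and withdrawals in Table 1.3 alongside EQ-5D and FAAM rows, and deaths in Table 4.1. The SAP is also descriptive only, with no hypothesis tests.

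This stands as far as it goes, and it rules out reading the plan as hiding these losses. It does not supply a label on the means or a link from the missing scores to their causes. Failures in Table 1.3 is undefined, and that shell omits the HOFFMANN LRF and T2 ICF systems.

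Three stronger readings are tempting, and the documents do not support them:
- **That no amputee has any later score.** Withdrawal is permissive in CIP 9.4 and SAP 6.3, and Table 3.3 allows an amputee to be assessed at 1 year and at the final visit. That row is a surgeon assessment, however, so it does not establish that questionnaires were completed.
- **That the means describe only saved limbs.** Scores taken before an amputation stay in earlier visits. They may also enter the final-visit column, which Table 1.1 labels as running from operation to 1 year.
- **That the scores are the leading secondary endpoint.** They are listed first, but neither document ranks the secondary endpoints.

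**Conclusion.** The point holds as a matter of selection and labelling. At visits after an amputation the summaries are likely to leave out amputees, and Tables 3.1 and 3.2 do not say so. A reader might infer that overstated benefit has been demonstrated. It has not: it is the likely direction, and it requires a worse change in amputees than in the rest.

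The size rests entirely on the assumed 15 to 25 point gap. The 1.5 to 4.3 points belong to the CIP's 3-year focus and should not be carried over to the current SAP. There, about 0.5 to 1.5 points pooled at 1 year is the relevant figure under constant hazard, and a small device group could be affected more by a single amputee. The effect is modest, and the change is worth making because it uses data already planned for collection.

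**What to change.** In SAP 9.2 and Tables 3.1 and 3.2:
- Keep the planned means, labelled as available-case (subjects with both a baseline and a visit score). State whether a pre-amputation score can count as the final visit.
- Beside each visit n, show how many subjects have no score because of amputation, death, sponsor termination or other reasons.
- Add a supplementary row with the number and percentage improved from baseline. Define improved. Take as denominator the subjects whose visit date fell before study termination, and count prior amputation as not improved. Show deaths separately, or count them under a stated rule consistent with CIP 9.4e, which treats death as device failure only when it is attributable to the device. State how subjects without a score for other reasons are handled.

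In Table 1.1, add rows for amputation, death and study terminated by sponsor.

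This needs no imputed scores and no new data collection. The cost is a little more table work and a somewhat less favourable improvement figure.

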## 11.3 REPORTS

### 11.3.1 Interim Analysis and Reports

Interim analyses will be performed on a yearly basis. The progress of the clinical investigation will be reported together with the interim results on the variable level according to the analysis plan. The only exception is the analysis of the primary endpoint will not be part of the interim reports.

### 11.3.2 Final Analysis and Reports

The full final report with complete analysis and progress and conduct reporting will be created at the end of this clinical investigation.

## 12 Clinical Investigation Plan Deviations

A CIP deviation is a departure from the approved CIP that is not implemented or intended as a systemic change. All CIP deviations are recorded and reported to the Sponsor and each site's IRB/EC in accordance with the respective site's IRB/EC policies. Investigators should not deviate from the study protocol except to deliver emergency care or to eliminate an immediate hazard to the subject.

## 13 Adverse Events

**An Adverse Event (AE)** means any untoward medical occurrence associated with the use of an intervention in humans, whether or not considered intervention-related

**A Serious Adverse Event (SAE)** is any AE that:

- Led to death
- Led to serious deterioration in the health the subject, that either resulted in
  - A life-threatening illness or injury, or
  - A permanent impairment of a body structure or a body function, or
  - In-patient or prolonged hospitalization, or
  - Medical or surgical intervention to prevent life-threatening illness or injury or permanent impairment to a body structure or a body function,
- Led to fetal distress, fetal death or congenital abnormality or birth defect.

**An Adverse Device Effect** is defined as any untoward or unintended response to the clinical investigation treatment; and/or a medical response which may have a causal relationship to the treatment.

- **An Incident** is defined as any malfunction or deterioration in the characteristics or performance of a device made available on the market, including use-error due to ergonomic features, as well as any inadequacy in the information supplied by the manufacturer and any undesirable side-effect.
- **A Serious Adverse Device Effect** is defined as any DRAE that results in consequences characteristic of a SAE or might lead to the consequences if suitable action or intervention is not taken; causes considerable interference with the subject's usual activities and may be

incapacitating or life-threatening, including those events resulting in a subject's disability or permanent damage, or required intervention to prevent disability or permanent damage; results in a life-threatening illness or injury; and/or results in death (fatal).

- **A Serious Incident** is defined as any incident that directly or indirectly led, might have led or might lead to any of the following:
  - the death of a patient, user or other person;
  - the temporary or permanent serious deterioration of a patient's, user's or other person's state of health;
  - a serious public health threat
- **An Unanticipated Adverse Device Effect (UADE)** is defined as an AE not described in the informed consent, CIP or device labeling which has resulted in any of the consequences of a SAE or which might have led to any of the consequences of a SAE if suitable action had not been taken, intervention had not occurred, or if circumstances had been less opportune. Anticipated AEs will be those listed in the HOFFMANN® LRF CIRCULAR EXTERNAL FIXATION, SALVATION™ EXTERNAL FIXATION SYSTEM, SALVATION™ FUSION BOLTS AND BEAMS, SALVATION™ 2 MIDFOOT NAIL, SALVATION™ 3DI PLATING SYSTEM, T2® ICF INTRAMEDULLARY NAILING SYSTEM, and VALOR™ ANKLE FUSION NAIL Systems device labeling (Surgical Technical Manual and IFU).

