10.1 Adverse Events

The safety of each device will be summarized in the final report. The overall summary of adverse events will be presented for each device. Total events, patient counts and percentages of adverse events for each device will be summarized for the following factors:

- i.) Procedure-Related Adverse Event / Incident.
- ii.) Device-Related Adverse Event / Incident
- iii.) Device Failure
- iv.) Serious Adverse Event (SAE)
- v.) Hospitalization SAE Outcome
- vi.) Treatment Required for the AE

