10.2 Serious Adverse Events

A separate summary table (or listing) of complications that met the serious adverse events (SAE) classification will be presented. Also, this section presents the narratives of each SAE that occurred in the clinical investigation. A serious adverse event (SAE) as defined from ISO 14155:2020(E) Clinical Investigations of Medical Devices for Human Subjects - Good clinical practice, is any adverse event that:

- a. Led to death,
- b. Led to a serious deterioration in the health of the subject, that either resulted in

- A life-threatening illness or injury, or
- A permanent impairment of a body structure or a body function, or
- In-patient or prolonged hospitalization, or
- Medical or surgical intervention to prevent life-threatening illness or injury or permanent impairment to a body structure or a body function.

c. Led to fetal distress, fetal death or congenital abnormality or birth defect.

The narrative for each SAE will be presented to describe the following:

- Nature and intensity of the event,
- Clinical course leading up to the event,
- Indication of timing relevant to test investigational device/product administration,
- Relevant laboratory measurements;
- Whether the treatment was stopped, and countermeasures (and timing);
- Post-mortem findings;
- Investigator's opinion on causality and sponsor's opinion on causality, if appropriate.

In addition, the following information will be included (if available) in the SAE narrative:

- Patient identifier;
- Age and sex of patient; general clinical condition of the patient, if appropriate;
- Disease being treated (this is not required if it is the same for all patients) with duration (of the current episode) of illness;

11 Reporting Conventions

All statistical output will have the following standard elements:

Stryker Corporation
US-20-SAL-001-FINS Page of

Title of Display
Clinical investigation Population
<BODY OF DISPLAY>

12 Summary of Changes to the CIP and/or SAP

No changes to the planned statistical analysis as indicated in the CIP.

13 Statistical Software

All statistical analyses will be performed using SAS version 14.1 or higher.

14 Listing of Tables, Listings, and Figures (TLF)

The listings of TLF are provided below with the link to the corresponding Table templates in Appendix 1.

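### The SAP does not visibly carry over the protocol's serious device-related endpoint, so foreseeable device effects with only potential for serious harm could be left out of serious reporting

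*Protocol*

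**What the plan says.** **Endpoint.** Protocol 11.2.4 names "serious device-related adverse effect (SDRAE") as a safety endpoint in its own right, alongside SAE, device-related effects, serious procedure-related effects and unanticipated adverse device effects (UADE). For each type it asks for total counts and per-subject rates with exact binomial 95% intervals.

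**Definitions.** In Protocol 13 an SAE is defined by what happened: death, serious deterioration in health, or fetal harm. One way to meet the deterioration criterion is "Medical or surgical intervention to prevent life-threatening illness or injury or permanent impairment to a body structure or a body function". A serious adverse device effect is "any DRAE that results in consequences characteristic of a SAE", or one that "might lead to the consequences if suitable action or intervention is not taken; causes considerable interference with the subject's usual activities". The interference wording does not stand alone: the sentence goes on to say that such an event can disable or threaten life, and gives lasting damage and preventive treatment as examples. The definition ends with life-threatening illness or injury, and death.

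**SAP.** SAP 10.1 lists the factors to be tabulated by device. Device-related events are one factor and "iv.) Serious Adverse Event (SAE") is another; none combines the two or uses the protocol's device-effect definition. The Table 4.1 shell likewise has Device-Related and Serious AE rows, and adds UADE, Unanticipated AE and Death rows that SAP 10.1 does not list. SAP 10.2 repeats the outcome-based SAE criteria and states: "A separate summary table (or listing) of complications that met the serious adverse events (SAE) classification will be presented". Its narratives are also for SAEs. SADE is in the SAP's abbreviation list but is not used in its analysis sections or in the shells I could read. SAP 12 says that the analysis planned in the protocol is unchanged.

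**The concern.** Two things go missing between the protocol and the SAP. The first is a named endpoint: the protocol asks for an SDRAE rate, and no visible SAP output gives one. The second is a definition: the protocol's serious device effect reaches potential harm, while every serious output described in SAP section 10 uses the SAE definition, which requires that the harm or intervention occurred.

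SAP 7 cancels hypothesis testing and SAP 9.1 cancels the three-year amputation analysis, so descriptive safety is one of the main results left. A device effect that the protocol calls serious, and that a site must notify within 24 hours under Protocol 13.3, could reach the final report without being counted or narrated as serious. With no change declared in SAP 12, a reader would not know that the endpoint had been dropped or narrowed.

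**Working it through.** No power or rate calculation applies. The check compares definitions and traces each kind of device effect to its place in the SAP.

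**Step 1: is a serious device effect always an SAE?** No. The first limb of the device-effect definition, SAE consequences that occurred, matches the SAE definition. The second limb, consequences that might follow without action, has no counterpart in the SAE criteria of Protocol 13 or SAP 10.2. The SAE intervention criterion comes close, but it is nested under serious deterioration in health. Action taken before any serious deterioration meets the device-effect limb and need not make the event an SAE.

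**Step 2: where does each kind of device effect appear?**

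| Device-related event | SAE? | UADE? | Visible SAP output |
|---|---|---|---|
| (a) SAE consequences occurred | Yes | Only if not foreseen | Device-Related and Serious AE rows; SAE table or listing; narrative |
| (b) Serious deterioration, with intervention to prevent life-threatening harm or permanent impairment | Yes | Only if not foreseen | As (a) |
| (c) Not foreseen; might have led to SAE consequences | Not necessarily | Yes | Device-Related and UADE rows |
| (d) Foreseeable; might lead to SAE consequences without action, but they did not occur | No | No | Device-Related row only |

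Group (d) is the gap. It is a plausible group, because a UADE must be absent from the consent form, protocol and labeling. Protocol 13.2 names infection, implant fracture, loosening requiring revision, and pseudarthrosis as foreseeable, so these cannot be UADEs.

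**Step 3: can SDRAE be recovered from the two rows?** No. Let D be the number of subjects in the Device-Related row, S the number in the Serious AE row and N the denominator. The number in both lies anywhere from max(0, D + S − N) to min(D, S), and a subject in both rows may have one non-serious device-related event and one unrelated SAE. Even an event-level cross of SAE with device-related gives only the device-related SAEs, as in (a) and (b), and misses (d).

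**Step 4: size.** The documents give no adverse event counts, so the size of group (d) cannot be computed. For scale only, SAP 4.1 gives about 42 implanted subjects, so one subject moves a pooled per-subject rate by 1/42 = 2.4 percentage points. That describes the study's size; it does not estimate the gap.

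**The case against.** The strongest reply is that little is lost. Group (d) events are still counted as device-related AEs and appear in the adverse event listing (Listing 12). Protocol 7.1 and SAP 4.2 describe the safety assessment as the incidence of device-related events, with no restriction to serious ones. The SAE intervention criterion and the UADE row already take up part of the wider definition. Table 4.1 holds rows that SAP 10.1 does not list, so SAP 10.1 is not exhaustive, and the shells of Tables 4.2 (device-related AEs) and 4.3 (SAEs) were not in the text available to me. Either could contain a seriousness breakdown. All of this stands. It limits the point to group (d) and to a possible omission, but it does not supply the SDRAE counts, rates and intervals that Protocol 11.2.4 asks for.

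A second reply is that the documents do not show that the AE form records seriousness by the device-effect definition; Protocol 13.1 mentions only relationship. That also stands, and it is why the fix needs the records to be re-read.

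A reader might go further in three ways that the documents do not support:

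- **That considerable interference with activities is by itself a lower threshold.** The sentence continues with the qualifier that the event may be incapacitating or life-threatening, and with examples that largely parallel the SAE criteria.
- **That device-related seriousness is understated.** The SAP states no serious device-related rate that could be too low, and it nowhere tells the analyst to cross SAE with device-related.
- **That expedited reporting is weakened.** The 24-hour rule in Protocol 13.3 refers to the device-effect category and is untouched by the SAP.

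**Conclusion.** The point holds in a limited form. A safety endpoint listed in the protocol has no visible counterpart in SAP 10.1, SAP 10.2 or Table 4.1, and SAP 12 does not record its absence. Because the protocol's serious device effect is wider than an SAE, SAE-only serious reporting could leave out foreseeable device effects that had the potential for serious harm but did not cause it. The size cannot be estimated, and it may be zero.

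The conclusion rests on two assumptions. First, SDRAE (Protocol 11.2.4 and 13.2), SADRE (Protocol 13.2 and 13.3) and serious adverse device effect (Protocol 13) are taken as one concept. Only the last is defined, but Protocol 13.2 uses SDRAE in its heading and SADRE in its text for what appears to be the same thing. Second, the shells of Tables 4.2 and 4.3 do not already contain the missing category. If they do, what remains is the scope of the narratives and the silence in SAP 12.

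**What to change.** Add a factor for serious adverse device effect / SDRAE, under the Protocol 13 definition, to SAP 10.1 and Table 4.1. Report the counts, per-subject rates and exact 95% intervals of Protocol 11.2.4; these are estimates and do not conflict with the SAP's decision against hypothesis tests. Identify the events from investigator reports, including the 24-hour notifications under Protocol 13.3, and not by crossing SAE with device-related. Include them in the SAP 10.2 listing and narratives whether or not they are SAEs, and say in SAP 10.2 that the two definitions differ.

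The alternative is to reconcile the two definitions and record in SAP 12 that the SDRAE endpoint has been dropped. In either case, settle on one label for the category.

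The cost is one table row, a few narratives and a re-read of the device-related AE records in about 42 subjects. The sponsor should already hold the notified events.
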